9.4. Medical and Surgical Procedures

Medical and surgical procedures will be coded using MedDRA, Version 25.0, March 2022.

Prior medical and surgical procedures are defined as those which have been stopped before first treatment.

- Procedure before informed consent signed is defined as those stopped before the date of informed consent signed to the study.
- Procedure during screening period is defined as those stopped on or after the date of informed consent signed until before first treatment date.

Concomitant medical and surgical procedures will be defined as those started or stopped on or after the first treatment, or were ongoing during the study. If a procedure is started before the first treatment but ongoing or stopped on or after the first treatment, it will be considered concomitant.

This document is confidential.

- Procedures during treatment period are defined as those started, stopped, or ongoing during the period.
 - Procedure during Initial Period is defined if started or stopped or ongoing during Initial Period.
 - Procedure during Maintenance Period is defined if started or stopped or ongoing during Maintenance Period.
 - If early discontinued during Initial (or Maintenance) Period, the treatment period will be defined from start of treatment till 4 weeks after the last treatment or early discontinuation date whichever is earlier.
- Procedures during follow-up period are defined as those started, stopped, or ongoing during the period.
 - Follow-up Period is defined if used from post treatment period to follow-up visit date.
 - Procedure during Follow-up Period will be summarized in accordance with the respective period (Initial or Maintenance).
- If procedure is being used continuously during both periods (e.g., started in the Initial Period and ended or ongoing in the Maintenance Period), it will be counted for each period.

If the stop date and 'ongoing' are missing then the procedure will be considered concomitant. If stop date is partially missing, the procedure will be considered concomitant unless the non-missing part of date proves it ended prior to the first treatment date.

The following medical and surgical procedures (prior, concomitant and rescue procedures) will be summarized by treatment group and period using the number and percent of subjects reporting each SOC and PT and sorted alphabetically by SOC and descending frequency of PT within SOC in the Nemoalizumab 30mg Q4W group. Summary tables will be presented for the ITT population.

- Prior procedure before screening (before informed consent date)
- Prior procedure before first dosing (from screening [informed consent date] before the first treatment)
- Concomitant procedure during treatment period (initial and maintenance)
- Concomitant procedure during follow-up period
- Rescue procedure during treatment period (initial and maintenance)
- Rescue procedure during follow-up period

Medical and surgical procedures listings and rescue procedure listing will be presented by treatment group for ITT population and sorted by subject number, start date, stop date, SOC, and PT.

9.5. Medication

Medications will be classified and summarized on the ITT population as follows:

- Prior medications are defined as those which stop before the first injection of study drug during the study.
 - Prior medication before informed consent signed is defined as those stopped before the date of informed consent signed to the study.
 - Prior medication during screening period is defined as those stopped during screening period (on or after the informed consent date until before the first treatment date).
- Concomitant medications are defined as those started or stopped on or after the first injection of study drug.

This document is confidential.

- Medication during treatment period are defined as those started, stopped, or ongoing during the period.
 - Medication during Initial Period is defined if started or ongoing or ended during Initial Period.
 - Medication during Maintenance Period is defined if started or ongoing or ended during Maintenance period.
 - If early discontinued during Initial (or Maintenance) Period, the treatment period will be defined from start of treatment till 4 weeks after the last treatment or early discontinuation date whichever is earlier.
- Medication during follow-up period are defined as those started, stopped, or ongoing during the period.
 - Follow-up Period is defined from post treatment period to follow-up visit date.
 - Medication during Follow-up Period will be summarized in accordance with the respective period (Initial or Maintenance).
- If medication is being used continuously during both periods (e.g., started in the Initial period and ended or ongoing in the Maintenance period), it will be counted for each period.

If the stop date and 'ongoing' are missing then the medication will be considered as concomitant medication. If stop date is partially missing, the medication will be considered as concomitant unless the non-missing part of date proves it ended prior to the first treatment date.

Medications (prior, concomitant and rescue medications) will be coded using Version B3 March 2022 of the World Health Organization's Drug Dictionary (WHO DD). Preferred Anatomical Therapeutic Chemical (ATC) coding will be performed.

The following summaries by ATC level 2, ATC level 4 and preferred term (PT) will be produced on the ITT population. Subjects with more than one medication in a given ATC level and preferred name will be counted only once in that category. It will be sorted ATC level alphabetically and descending frequency in PT within ATC level term.

- Prior medication before screening (before informed consent date)
- Prior medication before first dosing (from screening [informed consent date] before the first treatment)
- Concomitant medication during treatment period (initial and maintenance)
- Concomitant medication during follow-up period
- Rescue medication during treatment period (initial and maintenance)
- Rescue medication during follow-up period
- Background topical therapy (TCI/TCS) during treatment period (initial and maintenance)
- Background topical therapy (TCI/TCS) during follow-up period

All medications (prior and concomitant medications, rescue medications, background TCI/TCS will be listed for the ITT population. In addition background TCI/TCS dispensation and receipt will be listed for the ITT population.

9.6. Extent of Exposure

The extent of exposure will be summarized for the Initial Period and the Maintenance Period. Summary for Overall Treatment Period (from Initial to Maintenance Period) will be included in the Maintenance Period summary table.

This document is confidential.

The number of subjects exposed will be summarized for the Initial Period and Maintenance Period, and Overall Period (Initial + Maintenance).

- Treatment duration (in days) is calculated as follows, where date of first treatment is defined as the first day of the relevant study Period: [(date of last treatment – date of first treatment) + 1].
- Total number of doses administered will be calculated as the sum of all doses of study drug administered.
- Total number of doses planned will be calculated as the sum of all doses of study drug planned (dispensed) according to the treatment schedule of the treatment group. If a subject missed dosing due to skipped visit or completed a visit without dosing, this missed dose which is supposed to be dispensed will be accounted for the calculation.
- The number of subjects who missed at least one dose
- The number of subjects who missed at least one dose due to COVID-19*
- The number of doses missed
- The number of doses missed due to COVID-19*

**The reason for dose not administered reported in CRF is COVID-19 [This will be identified using Other specify field in CRF].*

9.7. Treatment Compliance

Treatment compliance will be assessed through the treatment records and drug dispensation logs. As study drug is administered in the clinic, treatment compliance will be overseen and documented by the investigator and study staff (using the treatment records and drug accountability records).

Treatment compliance(%) will be calculated by Period as total number of actual injections/ total number of expected injections *100.

This document is confidential.

10. Efficacy

The ITT population will be the primary population for all efficacy analyses. Both primary and key secondary and secondary endpoints of the Initial Period will be analyzed for the following populations:

- Full population which includes all subjects in ITT population
- Baseline PP NRS ≥ 7

All efficacy variables will be summarized by treatment group at each analysis visit, separately for the Initial Period and Maintenance Period. The primary comparison of interest is nemolizumab 30 mg compared to placebo for the co-primary endpoints in both populations (Full population; Baseline PP NRS ≥ 7).

To control the type I error at 5% significance level, a serial gatekeeping approach will be implemented. The co-primary endpoints will be tested at 2.5% significance level for each population. If both co-primary endpoints are statistically significant at 2.5% significance level, the key secondary endpoints will be tested sequentially following hierarchical testing procedure using the pre-specified order of endpoints for each population. The comparisons for key secondary endpoints will be made sequentially, and the subsequent tests will be stop when no statistical difference is found.

If $p < 2.5\%$ for all endpoints (co-primary and key secondary) in at least one population, then 2.5% will be recycled to test other population at 5% level of significance.

Other secondary endpoint comparisons will not be adjusted for multiplicity.

10.1. Primary Efficacy Endpoints and Analysis

10.1.1. Primary Analysis of Primary Efficacy Endpoint

Primary efficacy endpoint consists of the two co-primary endpoints:

- Proportion of subjects with an IGA* success (defined as an IGA of 0 [clear] or 1 [almost clear] and a ≥ 2 -point reduction from Baseline) at Week 16
- Proportion of subjects with EASI-75* ($\geq 75\%$ improvement in EASI from Baseline) at Week 16

* Further details regarding IGA and EASI-75 can be found in Sections 10.3.1 and 10.3.2 respectively.

Assessment results after taking rescue medication will be considered as treatment failure i.e. non-responders. Missing values at Week 16 will be treated as non-responder.

Both co-primary endpoints will be analyzed using a Cochran-Mantel-Haenszel test adjusted for the randomized stratification variables (IGA severity [3=moderate, 4=severe] and PP NRS [≥ 7 , < 7] for full population; IGA severity only for Baseline PP NRS ≥ 7 population) at 2.5% significance level (2-sided). In addition an unadjusted CMH test will be performed.

The proportion of subjects with IGA success and with EASI-75 at Week 16 will be summarized. The estimate of treatment unadjusted difference with the corresponding 2-sided 95% CI and strata-adjusted difference with the corresponding 2-sided 97.5% confidence interval, and p-values will be presented.

Bar charts for the proportions of subjects with IGA success and subjects with EASI-75 at Week 16 will be presented.

This document is confidential.

In addition, the proportion of subjects with IGA success will be analyzed using non-responder imputation on the ITT population excluding subjects who used the different version of IGA.

Additional summary tables for primary endpoints will also be presented by visit but excluding subjects from the visit summarized if the visit was affected by pandemic.

10.1.2. Sensitivity Analyses of Primary Efficacy Endpoint

The following sensitivity analyses for both populations will be conducted for the robustness of the primary analyses.

- Same analysis on PP population
- Tipping point analysis (see Appendix 22.1)
- Multiple imputation (MI) methods (see Appendix 22.1)
- Last Observation Carried Forward (LOCF) imputation method for missing data. Missing post-baseline values will be carried forward from the last non-missing post-baseline value. Baseline value will not be carried forward to post-baseline value.
- Observed Case (OC) - no data will be imputed. For this analysis, if any rescue medication is received, data post-rescue therapy will be analyzed as observed (i.e., not considered treatment failure).
- Same analysis on ITT using 'actual stratum' instead of 'stratum at the randomization'.

Tipping point analysis, multiple imputation methods, LOCF and OC analysis will be performed on the ITT population. Except OC analyses, assessments on or after rescue therapy used will be considered as treatment failure and will be considered as non-responders for analysis.

10.1.3. Subgroup Analyses of Primary and Key Secondary Efficacy Endpoints

In addition, the same analyses as described in Section 10.1.1 10.1.1 (with strata-adjusted 95% CI instead of strata-adjusted 97.5% CI) will be performed for the subgroups defined in Section 8.6.

The subgroup analyses will be performed on the ITT population (Full population; Baseline PP NRS ≥ 7) for primary and key secondary endpoints. Forest plot will be presented along with subgroup analysis results.

10.2. Key Secondary Efficacy Endpoints and Analysis

The same analyses as described in Sections 10.1.1, 10.1.2 and 10.1.3 will be performed for the key secondary endpoints on the ITT population (both Full population and population with baseline PP NRS ≥ 7). Key secondary endpoints are defined as follows:

- Proportion of subjects with an improvement of PP NRS ≥ 4 at Week 16
- Proportion of subjects with PP NRS < 2 at Week 16
- Proportion of subjects with an improvement of sleep disturbance NRS (SD NRS) ≥ 4 at Week 16
- Proportion of subjects with an improvement of PP NRS ≥ 4 at Week 4
- Proportion of subjects with PP NRS < 2 at Week 4
- Proportion of subjects with an improvement of PP NRS ≥ 4 at Week 2
- Proportion of subjects with an improvement of PP NRS ≥ 4 at Week 1
- Proportion of subjects with EASI-75 and improvement of PP NRS ≥ 4 at Week 16

This document is confidential.

- Proportion of subjects with IGA success and improvement of PP NRS ≥ 4 at Week 16. This endpoint may be analyzed using non-responder imputation on the ITT population excluding subjects who have incorrect version of IGA.

Same with primary endpoints, additional summary tables for key secondary endpoints will be presented by visit but excluding subjects from the visit summarized if the visit was affected by pandemic.

As a sensitivity analysis, summary tables for key secondary endpoints will be presented by visit but using weekly average PP/SD NRS with at least 2 non-missing diary and also with at least 3 non-missing diary, respectively. No analysis visit window extension at Week 16 applies.

Further details regarding IGA, EASI-75, PP NRS and SD NRS can be found in Sections 10.3.1, 10.3.2, 10.3.3 and 10.3.4.

In addition, forest plots will be presented for co-primary and key secondary endpoints on the ITT population.

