8.3.2 Inclusion Criteria

To be eligible for study entry, subjects must satisfy all of the following inclusion criteria:

1. Male or female subjects aged ≥ 12 years at the screening visit.

CONFIDENTIAL

Note: Enrollment of subjects aged 12 to 17 years has been opened after the IDMC has assessed interim safety data from the phase 2 study (Protocol 116912) and provided recommendations to the sponsor, who then determined the eligibility of this age group for enrollment in the study. The sponsor sent a written communication to the site confirming that the study is open for enrollment of adolescents. Adolescents could not be enrolled in the study until such communication was received.

2. Chronic AD for at least 2 years before the screening visit and confirmed according to American Academy of Dermatology Consensus Criteria ([Appendix 1](#))² at the time of the screening visit.
3. EASI score ≥ 16 at both the screening and baseline visits.
4. IGA score ≥ 3 (based on the IGA scale ranging from 0 to 4, in which 3 is moderate and 4 is severe) at both the screening and baseline visits.
5. AD involvement $\geq 10\%$ of BSA at both the screening and baseline visits.
6. Peak (maximum) pruritus NRS score of at least 4.0 at the screening and baseline visit.

Screening PP NRS score will be determined by a single PP NRS assessment (score ranging from 0 to 10) for the 24-hour period immediately preceding the screening visit.

Baseline PP NRS score will be determined based on the average of daily PP NRS scores (score ranging from 0 to 10) during the 7 days immediately preceding baseline (rounding is not permitted). A minimum of 4 daily scores out of the 7 days immediately preceding baseline is required for this calculation.

7. Documented recent history (within 6 months before the screening visit) of inadequate response to topical medications (TCS with or without TCI). All subjects must demonstrate inadequate response to TCS. All subjects who have used TCI within 6 months of the screening visit, or for whom TCI is selected as background therapy for sensitive areas, must also demonstrate inadequate response to TCI. Acceptable documentation includes patient records with information on TCS (with or without TCI) prescription and treatment outcome, or written documentation of the conversation with the subject's treating physician, if different than the investigator. If documentation is inadequate, subjects may be re-screened after such documentation is obtained.

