4.3. Determination of Sample Size

With a 2:1 randomization, 180 subjects in nemolizumab and 90 subjects in placebo required to detect the differences in both co-primary endpoints to achieve 90% power.

IGA Success: To detect a difference of 18%, assuming IGA response for nemolizumab 30% and placebo 12% at Week 16.

EASI-75 Response: To detect a difference of 30%, assuming EASI-75 response for nemolizumab 49% and placebo 19% at Week 16.

To ensure sufficient exposure with nemolizumab and to ensure sufficient size of the safety database, the sample size increased to 750 subjects in total with randomization ratio 2:1. This sample size will provide more than 99% power to detect the treatment difference for both co-primary endpoints at 2.5% significance level.

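### SD NRS improvement ≥4 is tested in all ITT subjects with no baseline SD NRS minimum; adding baseline SD NRS as a CMH stratum recovers part of the power lost, and the estimate needs a supportive analysis

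*SAP*

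**What the plan says.** The endpoint is "Proportion of subjects with an improvement of sleep disturbance NRS (SD NRS) ≥ 4 at Week 16" (SAP 10.2). SAP 10.2 and Table 7-3 place it in the ITT population, for both the full population and the baseline PP NRS ≥7 population. Neither attaches a condition on baseline SD NRS.

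Protocol 8.3.2 requires "Peak (maximum) pruritus NRS score of at least 4.0 at the screening and baseline visit" and also sets minimums for EASI, IGA and BSA. None of the twelve inclusion criteria mentions SD NRS, which runs from 0 to 10 (Protocol 9.1.4).

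SAP 10.2 applies the co-primary analysis of SAP 10.1.1, a "Cochran-Mantel-Haenszel test adjusted for the randomized stratification variables". The strata are IGA and PP NRS in the full population and IGA alone in the PP NRS ≥7 population. SAP 10.1.1 also asks for a strata-adjusted difference with a 97.5% CI.

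On alpha, the opening of SAP Section 10 states: "The co-primary endpoints will be tested at 2.5% significance level for each population". Key secondary endpoints then follow in fixed order and testing stops at the first failure. If every co-primary and key secondary endpoint succeeds in one population, its 2.5% passes to the other, which is then tested at 5%.

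Baseline SD NRS is not a subgroup in SAP 8.6. No Initial Period SD NRS output in the table index is limited to subjects with baseline ≥4. SAP 10.3.4, to which 10.2 refers for SD NRS detail, is redacted.

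**The concern.** For itch, the entry rule makes a 4-point fall arithmetically possible for everyone. For sleep it does not: a weekly average below 4 cannot drop by 4 on a scale that ends at 0. These subjects are known before treatment to be non-responders in both arms, yet they are analysed together with subjects who can respond.

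This has two effects. The test loses power, and the ITT difference is smaller than the effect in subjects with sleep disturbance to lose. The first matters because six endpoints follow SD NRS in the sequence, and because the SAP states power only for the co-primary endpoints. The continuous analysis does use baseline: the MMRM example in SAP 22.2 includes it, and the table index lists an MMRM for SD NRS change. The responder test, which carries alpha, does not.

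**Working it through.** **Inputs from the documents.** Two-sided 2.5% per population (SAP 10, 10.1.1), so z = 2.2414. N = 750 at 2:1, that is 500 and 250 (SAP 4.3). At least 250 subjects in each PP NRS stratum (SAP 4.1), so the PP NRS ≥7 population can range from about 250 to 500.

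**Assumptions, not in the documents.** q, the share with baseline SD NRS ≥4, is 0.9 to 0.6. Response among those who can respond is 40% vs 25%, with 40% vs 20% and 35% vs 20% as alternatives.

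**Formula.** Power = Φ[(Δ − z·s0)/s1], where s0 is the pooled and s1 the unpooled standard error of the difference.

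**Plan's own figure.** SAP 4.3 says: "This sample size will provide more than 99% power to detect the treatment difference for both co-primary endpoints at 2.5% significance level". For IGA (30% vs 12%): pooled rate 0.24, s0 = √(0.24×0.76×(1/250+1/500)) = 0.0331, s1 = √(0.12×0.88/250 + 0.30×0.70/500) = 0.0290. Power = Φ[(0.18 − 0.0741)/0.0290] = Φ(3.65) = 99.99%. EASI-75 exceeds this. The stated figure reproduces.

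**Why the stratum works.** A stratum without responders contributes zero to both the CMH numerator and its variance. The stratified test therefore equals the test on the qN subjects who can respond. The planned test uses all N with rates diluted to q·p.

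**Example, 750 subjects, 40% vs 25%, q = 0.7:**
- Planned: 28% vs 17.5%, Δ = 0.105, s0 = 0.0333, s1 = 0.0313; Φ(0.97) = 83.4%.
- Stratified: 350 vs 175 subjects, Δ = 0.15, s0 = 0.0442, s1 = 0.0419; Φ(1.22) = 88.8%.
- If everyone could respond: 500 vs 250, Δ = 0.15, s0 = 0.0369, s1 = 0.0351; Φ(1.92) = 97.2%.

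**Range, 40% vs 25%, 2.5% level** (planned → stratified, %):

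| Below 4 | 750 subjects | 500 subjects | 250 subjects |
|---|---|---|---|
| 10% | 94.5 → 95.5 | 80.8 → 82.9 | 46.8 → 49.3 |
| 20% | 90.0 → 92.8 | 72.9 → 77.7 | 39.6 → 43.9 |
| 30% | 83.4 → 88.8 | 63.8 → 71.2 | 32.7 → 38.4 |
| 40% | 74.3 → 82.9 | 53.7 → 63.5 | 26.3 → 32.7 |
| None | 97.2 | 87.1 | 54.3 |

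Before rounding, the gains are 1.0–8.7, 2.2–9.7 and 2.4–6.4 points. As a share of the gap to the last row they are 37–39%, 29–34% and 23–32%.

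**Why only part is recovered.** Stratifying raises the signal-to-noise ratio by √[(1 − q·p̄)/(1 − p̄)], where p̄ is the pooled response rate. With p̄ = 0.35 and q = 0.7 this is 1.078. The loss from having only qN informative subjects, a factor √0.7 = 0.837, remains.

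**Other rates.** At 40% vs 20% and 750 subjects, the gain is 0.0–2.1 points; with 30% below 4 it is 98.7 → 99.5. At 35% vs 20% and q = 0.7, power is 88.0 → 91.7 with 750 subjects (98.3 if all could respond) and 36.5 → 41.5 with 250 (58.4 if all could respond).

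**Simulation check** (35% vs 20%, planned strata, 40,000 runs per case). With 60% able to respond in two of the four full-population strata and 90% in the other two: 90.7 → 93.2, against 98.3 if all could respond. PP NRS ≥7 with 250 subjects and q = 0.7: 37.4 → 42.5, against 59.2. Simulated type I error was 0.023–0.026.

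**Estimate.** A 15-point effect in subjects who can respond appears as 0.7 × 15 = 10.5 points in ITT. Stratifying does not change this, because the zero-response stratum keeps its weight in the adjusted difference.

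**The case against.** The planned test is valid. It uses the randomization strata uniformly across the co-primary and key secondary endpoints and matches the ITT estimands in Table 7-3. A reader might infer bias or inflated type I error; nothing in the documents or the simulation supports that. The point concerns efficiency and interpretation only.

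A reader might also infer that the added stratum restores the lost power, as if subjects below 4 only added variance. It does not: most of the loss is missing informative sample, which no stratum replaces.

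A reader might infer that failing SD NRS ends the sequence outright. SAP Section 10 qualifies this: if the full population succeeds on every endpoint, the PP NRS ≥7 population is retested at 5%. With 500 subjects, 40% vs 25% and 30% below 4, planned power is then 74.3% rather than 63.8%, and the gain from stratifying is 6.1 rather than 7.4 points. The same rule also works the other way: an SD NRS failure in one population prevents it from passing alpha on.

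The sleep effect may also be large. Protocol 6.2.3 reports p<0.001 for SD NRS at all three doses in phase 2b. That was at Week 24, in subjects with PP NRS ≥7, and the scale of analysis is not stated, so it fixes no Week 16 responder rate. It does mean that a modest effect cannot be taken for granted, and with a large effect the full-population gain is small. If low SD NRS goes with low PP NRS, the planned strata already capture some of the difference; the simulation with unequal shares still shows a gain.

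**Conclusion.** The point stands as a minor, inexpensive improvement. The text confirms that the endpoint is tested in all ITT subjects, that no SD NRS minimum applies at entry, and that the CMH strata do not separate subjects who cannot respond.

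Under 40% vs 25% with 10–40% below 4, stratifying gains about 1–9 points with 750 subjects and about 2–10 points in a PP NRS ≥7 population of 250–500, roughly a quarter to two-fifths of the loss. Under 40% vs 20% the full-population gain is about 2 points or less. There the recovered share is higher, but only because power is near its ceiling and the loss is under 4 points. If few subjects start below 4, the change hardly matters in the full population.

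The share below 4 and the response rates are assumptions. SAP 10.3.4 is redacted, so it may already contain something relevant. Failing SD NRS stops the remaining six tests in that population unless alpha is recycled from the other.

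**What to change.** For the SD NRS responder tests, pre-specify before unblinding:

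- Baseline SD NRS (<4, ≥4) as an additional CMH stratum, with the ITT denominator, endpoint and alpha unchanged.
- The stratum for subjects without a baseline SD NRS. SAP 8.2 needs 4 of 7 diary days, Table 8-2 allows up to 7 further days, and eligibility does not require the score. Improvement cannot be computed for these subjects, so under non-responder imputation they too are non-responders. Placing them with <4 would keep that stratum free of responders.
- As supportive output, response rates and the risk difference with CI among subjects with baseline ≥4, in both populations, because the ITT adjusted difference stays diluted.

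Stating the expected share with baseline ≥4 and the resulting SD NRS power in each population would also help.

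The cost is one extra factor from a baseline value that is already derived and summarized (SAP 8.2, 9.2), plus one supportive table. Strata double from 4 to 8 in the full population and from 2 to 4 in PP NRS ≥7, so they are somewhat sparser.
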